The obstetrical population is considered vulnerable. Pregnancy involves multiple interactions with the health care system and eventually all are admitted to the hospital for delivery, therefore, managing pregnant population presents a unique challenge during this pandemic. Additionally, the physiological changes and partial immune suppression during pregnancy makes the pregnant women and newborn babies susceptible to several infections. Post-partum hemorrhage, maternal sepsis, preeclampsia, premature rupture of membrane are the most common adverse events reported to have caused by this disease in pregnant women (11).

There are currently limited data on fCOVID-19 infections during pregnancy. Anecdotal evidence suggests that pregnant women do not appear to be different than the general population in terms of disease transmission. In addition, neonatal vertical transmission has been suspected in a neonate of a COVID-19 positive mother (12). Recently, poor maternal and neonatal outcomes including critical care admission, preterm normal and cesarean delivery, premature rupture of the membrane or PROM , fetal distress, stillbirth, and multiple organ dysfunction (1,11,13-17).

Importance of Registry

From the limited information gathered about the novel coronavirus, its impact on pregnancy and newborn and the drastically increasing burden of the disease, it is vital that scientific information concerning the disease is collected and shared in a concise and practical manner. Hence, there is a need to collect case data rapidly, to pool global data on the natural history of women affected by suspected COVID-19 or confirmed SARS-CoV-2 in pregnancy to inform treatment and implement preventative strategies in this and future outbreaks. A centre-based registry, gathering case data prospectively on the effect of SARS-CoV-2 infection from healthcare systems around the world offers a method to accrue clinical outcomes on key research questions from a variety of populations and the Q-PRECIOS register will serve such purpose.

4. Objectives

In this section provide a clear statement of the primary and any secondary objectives of the study

The main aim of this study is to understand the natural course of the COVID-19 infection during pregnancy and postnatal period. To this end the registry objective are to:

1. To form a disease registry linked with other national data sources for women with suspected COVID-19 or confirmed SARS-CoV-2 in pregnancy and their neonates.

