 - 1.1 Study the course of COVID-19 disease i.e. its symptoms, duration, progression in pregnant women
 - 1.2 Study the pregnancy, postnatal and neonatal effect of COVID-19 disease

Objective justification

The in-utero exposure of acute viral infection in some instances is proven to have short- and long-term neonatal effect during the postnatal and childhood period and the Zika virus, measles, mumps and rubella are few examples. COVID-19 is caused by a novel coronavirus strain of unknown consequences. The main purpose of this registry is to collect a baseline data and help establishing future studies and hypothesis generation.

In addition, we will be exploring the psychological impact of COVID-19 on women during the pregnancy and postnatal period. Stress and anxiety level are increased with potential adverse pregnancy and/or neonatal outcomes especially during infectious disease outbreak. In fact, COVID-19 is associated with adverse maternal and neonatal outcomes resulting in increased level of stress and anxiety. In addition, women during the pregnancy, peripartum, and postpartum period are at increased risk of depression. A risk that has been aggravated by social and physical isolation. Indeed, the social and physical isolation, a critically needed measure to stop the virus transmission, resulted in increased stress and depression level and adversely affecting the mental and physical health of both the mother and the baby.

5. Indicate if this is a retrospective data review

- **Retrospective Chart/data Review**
- **Provide the date range of the chart review**

6. Study Methodology

This is a nationwide prospective observational registry linked with PAN-COVID UK register of pregnant women with suspected and/or confirmed diagnosis of COVID-19 infection. The enrollment period for this registry is 2 years e.g. May 1, 2020 to May 1st, 2022. Case reports or cases diagnosed ever since 27th Feb will also be included. The authors of published case reports will be contacted for permission. This registry will open for enrollment after IRB/MRC approval. Understanding the effect of COVID-19 infection on pregnancy and its outcome is imperative to help the patients and healthcare providers understand the impact of the disease on the pregnant women and their offspring. There is no intervention planned in this study, therefore, there is a minimal risk associated with this study.

Data collection:

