Objective 1: To form a disease registry **linked with other national data sources** for women with suspected COVID-19 or confirmed SARS-CoV-2 in pregnancy and their neonates.

Objective 1.1: Study the course of COVID-19 disease i.e. its symptoms, duration, progression in pregnant women

Objective 1.2: Study the pregnancy and neonatal effect of COVID-19 disease

We will collect information about patient demographic, co-morbidities, clinicopathological information, COVID-19 disease sign, symptoms and its treatment, pregnancy and neonatal outcomes, and women mental health during pregnancy and postnatal period. Regarding pregnancy outcomes, our study will focus on miscarriage, fetal growth restriction and stillbirth, pre-term delivery and vertical transmission and will include fields on ultrasound diagnosis and neonatal care (for details refer to appendix 1, 2 and 3). The woman and her neonate(s) will be followed for 1 year postnatally. Regarding the neonatal outcomes, outlined in the neonatal outcome data collection sheet, includes birth weight, congenital malformations, APGAR score, Breastfeeding, COVID-19 status, respiratory symptoms, neonatal status, and discharge status.

Baseline characteristic and initial assessment will be done during the hospital admission up on COVID-19 diagnosis. Apart from that, there are 7-10 expected follow up telephone calls or online forms to be sent to the patient. The schedule and timeline of data/biospecimen collection are described in table 1.

Data Collection Form or Questionnaire	Baseline	Weekly for 4 weeks	2 nd Trimester (GA 24 weeks)	3 rd Trimester (GA 34 weeks)	GA 36 weeks	GA 38 weeks	6 weeks postpartum	6 Months	12 Months
Demographics, Health History and COVID-19 Questions	X								
COVID-19 Symptoms Follow-up		X	X	X			X	X	X
Pregnancy Status/Outcomes		X	X	X	X	X	X		
Depression and Anxiety*	X		X	X			X	X	X
Neonatal/Infant Outcomes							X	X	X

*Generalized Anxiety Disorder 7-item (GAD-7) scale and Edinburgh Postnatal Depression Scale (EPDS)

7. Study Population and Study Setting/ Location

We will include all pregnant patients with suspected or confirmed COVID-19 infection at all HMC facilities including WWRC, CH, AKH, AWH and its associated quarantine sites and their offspring's. The inclusion criteria are:

1. pregnant woman with suspected or confirmed SARS-CoV-2 infection
2. postpartum women who delivered during the last six weeks and
3. neonate(s) of women included in the registry.

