The maximum follow-up period is 2 years. Based on the gestational age at time of enrolment might vary e.g. if the patient was enrolled early in pregnancy e.g. during the first trimester, the enrollment period will be for 2 years whilst patient who is enrolled in third trimester will be enrolled for less than 2 years.

During the follow up, patient will be contacted over the phone.

Further, we aim to collect data about psychological status i.e. depression and anxiety disorders using the depression Edinburgh Postnatal Depression Scale (EDPS) and the Generalized Anxiety Disorder 7 (GAD-7) surveys. Both surveys, the EDPS and GAD-7, are self-administered surveys that will be sent through an SMS link to the subject. In case patient was identified as having depression or anxiety disorder, the patient will be referred to contact the national mental health helpline at [name]. In case the study team is concerned about the mental health of the subject a direct referral will be sent through Cerner and psychiatrist will be consulted.

Informed Consent

a) *How people will be **NOTIFIED OR APPROACHED** to consider being a research subject in this study?*

Patient will be notified through:

1. Advertisements such as hospital posters and social media. In this case, filling the study online form will be considered as a patient consent.
2. Referral through the primary physician. In this case, the primary physician will explain the study to the patient and document her willingness to participate in Cerner.

b) *Describe the **CONSENT PROCESS** procedures (When, Where, How, by Whom).*

When an eligible patient is referred by her primary physician, a study coordinator will follow-up by phone to explain the study and obtain a verbal consent to release medical information. In case of self-referral, through filling the online form or calling the study coordinator, a study coordinator will follow with a phone call to explain the study and obtain a verbal informed consent.

c) *Describe **HOW LONG** potential participants will have to decide on participation.*

The patient will be given a 24-hour period to decide.

d) *Describe how subjects will be **SCREENED FOR ELIGIBILITY** for the study.*

Patients will be screened based on a confirmatory laboratory result of a positive SARS-CoV-2 PCR results.

e) *Describe how subjects will be **ENROLLED** into the research study below.*

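### Section 7 admits women with suspected or confirmed infection, Section 8 screens on a positive PCR, and the plan does not say which entry rule governs

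*Combined protocol and SAP*

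**What the plan says.** **Passages that admit suspected women**

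- Section 4, Objective 1 (repeated under Data collection in Section 6) sets up the registry for "women with suspected COVID-19 or confirmed SARS-CoV-2 in pregnancy and their neonates".
- Section 7, lead sentence: "We will include all pregnant patients with suspected or confirmed COVID-19 infection at all HMC facilities".
- Section 7, first inclusion criterion: "pregnant woman with suspected or confirmed SARS-CoV-2 infection".
- Section 8, Study procedure: both suspected patients and those with positive results are found through Cerner. They are then approached through the primary physician, consented, and have baseline data collected. No laboratory step stands between identification and consent.

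**Passages that require a laboratory result**

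- Section 8, Informed Consent, item d, on screening for eligibility: "Patients will be screened based on a confirmatory laboratory result of a positive SARS-CoV-2 PCR results".
- Section 8, Informed Consent, item e, on enrolment: a woman's details go into the database, and she gets a study number, after the laboratory result is confirmed and verbal consent is given.

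**A third version**

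- Section 8, Data Collection, Management & Confidentiality, item a: the study number and registry entry follow informed consent, with no laboratory condition.

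**Analysis**

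- Section 9 counts positive patients in the prevalence numerator. It says nothing about infection status for any other summary.

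**The concern.** The entry rule fixes the population that every percentage in the registry describes. Here the passage headed as the study population and the passage on eligibility screening disagree about women who are suspected but have no positive PCR.

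The two possible consequences are alternatives.

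- **Items d and e govern.** The registry omits a group that Objective 1 and Section 7 say it will include. The percentages then describe confirmed women only, and no mixing arises.
- **Section 7 governs.** Women who never had SARS-CoV-2 may enter the denominators for symptoms, pregnancy and neonatal outcomes, and mental health. Those summaries are meant to describe COVID-19 in pregnancy.

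There is also a practical risk. Recruitment runs across several HMC facilities and quarantine sites, and each woman's primary physician collects the baseline data. Different staff could apply different rules, and the enrolled population would then be neither of the two described.

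**Working it through.** No arithmetic settles this point, so the check is a comparison of the passages.

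**Step 1. Apply each rule to each type of woman (consent given in every case).**

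| Woman | Objective 1, Section 7, Study procedure | Items d and e read together | Coding answer (item a) |
|---|---|---|---|
| PCR positive | enters | enters | enters |
| Suspected, result pending | enters | waits for the result | enters |
| Suspected, never tested | enters | cannot enter | enters |
| Suspected, PCR negative | depends on what suspected means | cannot enter | enters |

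The rules agree only on the first row. The last row cannot be settled from the text, because nothing says whether a negative test ends the suspicion.

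**Step 2. Look for a passage that reconciles them.** None was found. The nearest text to a case definition is in the sample size paragraph of Section 7. It lists symptoms, travel and contact with a case as the basis for diagnosis in Qatar. It does not call this a suspected case and does not link it to eligibility. The appendices are listed by title only, so the finding is limited to the supplied text.

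**Step 3. Sort out which passages carry weight.**

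- Item e does not itself mention a positive result. It takes that condition from item d.
- Section 6 describes a registry linked with the PAN-COVID register of "pregnant women with suspected and/or confirmed diagnosis of COVID-19 infection". The phrase may describe PAN-COVID and not this registry, so it is not counted on either side.
- The Importance of Registry text speaks of the need "to pool global data on the natural history of women affected by suspected COVID-19 or confirmed SARS-CoV-2 in pregnancy". That is a statement of purpose, not an entry rule.

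The conflict stands on Objective 1, Section 7 and the Study procedure against items d and e.

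**Step 4. Follow the conflict into the analysis.** The Outcomes text in Section 8 lists prevalence, presenting signs and symptoms, adverse pregnancy and neonatal outcomes, and mental status. Prevalence is protected by its numerator in Section 9. The other outcomes are tied to COVID-19 either in their own wording or, for pregnancy and neonatal outcomes, through Objective 1.2. None is tied to a positive test by an analysis rule.

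**Step 5. Size.** The change in a pooled percentage would be the suspected-only share multiplied by the difference between suspected-only and confirmed women. The plan gives neither input. Its anticipated 170 to 200 cases per month is not split by confirmation status, and the 15% positivity it cites says nothing about suspected women without a positive test. The effect cannot be computed.

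**The case against.** The strongest reply is a staged reading: suspected women are found in Cerner, then tested, and only positives are entered. This fits the order of Section 8 reasonably well. It does not fit Section 7, where suspected infection is itself a ground for inclusion, nor the Study procedure, where consent and baseline collection follow identification with no test in between.

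A second reply is that item d is only consent-form text. But it answers the form's direct question on how eligibility is screened, and item e answers how subjects are enrolled. Staff could reasonably work from both.

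A third reply is that the coding answer concerns data handling and leaves the laboratory condition unsaid. That is plausible, but the sentence still describes entry to the registry and should agree with the rest.

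A fourth is that baseline timing points to confirmed women: "Baseline characteristic and initial assessment will be done during the hospital admission up on COVID-19 diagnosis". This is weak evidence, because the plan elsewhere describes diagnosis in terms of symptoms, travel or contact, so diagnosis is not clearly PCR-based.

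It is also fair to say that this is a descriptive, hypothesis-generating registry. That limits how serious the point is but does not remove it, since description depends on knowing who is described.

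**Conclusion.** The point holds. The plan states entry rules that cannot all be followed, and the choice between them decides who is in the symptom, pregnancy, neonatal and mental-health percentages. Prevalence is not affected. The size of the effect is unknown and cannot be derived from the documents.

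Some stronger readings are tempting and are not supported:

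- **That the results will be distorted by a given amount.** Any figure would rest wholly on assumed shares and differences.
- **That the registry will both lose suspected women and mix them in.** One rule produces the first consequence and the other produces the second.
- **That adverse pregnancy and neonatal outcomes are certain to be pooled over uninfected women because their wording carries no infection qualifier.** Objective 1.2 supplies one. What is missing is an analysis rule, for these outcomes and for the symptom and mental-health ones alike.
- **That the plan nowhere defines a suspected case.** This is established only for the supplied text.
- **That a majority of passages settles which rule is right.** The Section 6 wording is ambiguous, and the direction is for the sponsor to decide.

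The verdict assumes only that items d and e are read together and that the passages mean what they say.

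**What to change.** Bring Objective 1, Section 7, the Study procedure, items d and e and the coding answer to a single entry rule. While doing so, make clear whether the Section 6 phrase describes this registry or PAN-COVID.

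If suspected women are kept:

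1. Define a suspected case in Section 7, including what happens to a woman whose PCR is pending, negative or never done.
2. Confirm that the mother's PCR status is captured on the case report forms, or add the field. The supplied text names COVID-19 status among the neonatal outcomes but does not show a maternal PCR field.
3. State in Section 9 that the main COVID-19 summaries use PCR-confirmed women, and that suspected women without a positive PCR are reported separately.

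If only PCR-confirmed women are wanted, narrow Objective 1, Section 7 and the Study procedure to match items d and e. The registry then gives up the suspected women it now names.

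The cost is a few sentences, possibly one data field, and no extra visits. Keeping suspected women but analysing them separately makes the main analysis set somewhat smaller than a pooled one, by an amount that the documents do not allow to be calculated.

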Once the laboratory result is confirmed and verbal consent is obtained, patient details will be entered into the online study database and given a study number.

Risk

The is a prospective observational registry. There minimal risk of breach of patient confidentiality. To minimize this risk, data will be entered into an electronic registry software. The software will be secured with username and password and only accessible by the study investigators for data entry. Data extraction will only be accessible to study PIs and co-PIs. Paper based data collection sheet will be secured in locked cabinets accessible only by study PIs and co-PIs. Only de-identified data will be shared amongst investigators. If a breach in confidentiality occurs, the IRB will be notified immediately. Consent form containing the linking information between collected data and patient's identifiable information will be stored in a locked cabinet and/or password locked computer. Information on the password protected computer database will only be accessed by the investigators. Furthermore, the PI's office will remain locked. All study documentation will be stored according to the MRC guidelines

Bio-Specimens & Sample Collection

NA

Outcomes

We believe the results of this study will generate robust data. Prevalence of SARS-CoV-19 infection in pregnancy. Percentage and distribution of COVID-19 presenting sign and symptoms. Percentage of adverse pregnancy and neonatal outcomes. Description of mental status of pregnant women affected by COVID-19 infections.

Data Collection, Management & Confidentiality

a) Indicate below HOW study data will be collected for the proposed research.

Study Forms Study Database Study Web-Based/App Other

Please detail how study data will be coded:

Once informed consent is obtained, patient will be given study number and entered in the registry system. Data will be stored registry database/web-portal password protected on Cerner. Only study investigators have access for data entry. For follow up purposes, study investigators will have access to the identifiable information during the data collection period. No individual identity will be disclosed in results and publications.

b) Describe below WHERE and HOW the study data is physically stored.

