Data collection/entry: HMC physicians will be eligible to enter patient initial assessment form. Follow up data study investigators and research coordinators will have access to enter patient data into the database.

Data extraction for audit, analysis, report and request of collaboration:

Data extraction access will be granted to specified personnel designated by the register steering committee.

e) Describe below HOW the study data is accessed.

Level access will be employed from HMC Cerner team. Study data will be accessed using a dedicated username and password for specified members.

f) Will subject identifiers be shared outside of HMC? If YES describe below WHOM the study data is shared

No, only deidentified data will be shared.

Subject Withdrawal/ Withdrawal of Consent

In case patient wish to be withdrawn from the study, no further contact will be made. However, collected information up to the point of withdrawal will be included in the analysis. Subjects withdraw from the study will be asked whether they are willing to allow ongoing data collection and his response will be recorded.

9. Statistical Consideration and Data Analysis

Descriptive data: Numerical data will be presented as mean and standard deviation where normally distributed or median and range where it's not normally distributed. Categorical data

will be presented as frequency and percentages. Prevalence of COVID-19 will be calculated as total number of patients who were positive over total number deliveries in the same month. Inferential analysis will be used to assess association and tests will be selected according to suitability.

10. Adverse Event Reporting

This is an observation study. There are no anticipated adverse events.

11. Ethical Consideration.

The registry will only commence after obtaining approval from IRB/HMC in accordance with good clinical practice, and MoPH regulations

12. Sponsor, Funding & Collaborator Information

MRC

13. Dissemination of Results and Publication policy

Once the project is funded, the study team will initiate monthly meetings to discuss study plans and patient recruitment. Team leaders will also meet monthly to share study updates. Furthermore, the study results will be shared among peers in the department through presentation of study findings. Finally, once the study is completed, we aim to present our findings at the Hamad Medical Corporation Annual Research Day, local and international conferences and in peer-reviewed journals.

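### Pregnancy outcomes are to be given as crude percentages with no risk set, so the miscarriage figure would depend on when women entered the registry

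*Combined protocol and SAP*

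**What the plan says.** Section 6 (Data collection) states that "our study will focus on miscarriage, fetal growth restriction and stillbirth, pre-term delivery and vertical transmission". Section 8 (Outcomes) turns this into "Percentage of adverse pregnancy and neonatal outcomes". For categorical data, Section 9 says that they "will be presented as frequency and percentages". The only denominator it gives is for another quantity: "Prevalence of COVID-19 will be calculated as total number of patients who were positive over total number deliveries in the same month".

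Entry is wide. Section 7 admits a "pregnant woman with suspected or confirmed SARS-CoV-2 infection" without a gestational limit, and "postpartum women who delivered during the last six weeks and" neonates of enrolled women. The postpartum criterion does not say whether infection came before or after delivery. Section 8 accepts enrolment from the first to the third trimester. Section 6 adds that "Case reports or cases diagnosed ever since 27th Feb will also be included". The sample size text in Section 7 says that testing is selective except at caesarean section, where every woman is screened.

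No visible section gives a gestational limit for miscarriage or preterm delivery, a rule for late entry, or an expected distribution of gestation at entry.

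**The concern.** Miscarriage can happen only up to a gestational limit, and a registry sees only losses that follow entry unless it takes in women after the loss. Two separate mechanisms then act on a crude percentage.

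- **Left truncation.** A woman who enters at 18 weeks has already survived most of the period in which she could miscarry. Even among women still at risk, the percentage is a risk from entry onward, not a whole-pregnancy risk.
- **Dilution.** If all enrolled women are counted, those who enter after the limit or after delivery add to the denominator but cannot add to the numerator.

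Section 4 says: "The main purpose of this registry is to collect a baseline data and help establishing future studies and hypothesis generation". A miscarriage percentage that mainly reflects entry timing is a poor baseline. It could look reassuring beside a background rate even if infection raised the risk.

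**Working it through.** **Plan's own figure.** There is none to reproduce. The documents give no miscarriage rate, gestational limit or entry pattern, so every size below rests on assumptions.

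**Inputs from the documents.** Entry at any gestation and up to 6 weeks postpartum (Sections 7 and 8); universal screening at caesarean section (Section 7, sample size).

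**Assumptions.** Miscarriage limit c = 20 or 24 weeks; uniform entry from week s to delivery at week e, plus 6 weeks; infection at entry; no infection effect.

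**Step 1, identity.** If nobody enters after a loss, the numerator is the same for both denominators, so

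all-enrolled % = at-risk % × share of entrants still at risk.

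This holds whatever the miscarriage risk.

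**Step 2, the share.** Ignoring the few pregnancies lost before entry, share = (c − s)/(e − s + 6).

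- s = 4, e = 39: 16/41 = 39.0% (20 weeks) and 20/41 = 48.8% (24 weeks).
- Lowest for s = 0 to 12 and e = 38 to 40: s = 12, e = 40, c = 20 gives 8/34 = 23.5%.
- Highest: s = 0, e = 38, c = 24 gives 24/44 = 54.5%.

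So the range is about 24% to 55%.

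**Step 3, clustering at delivery.** If a fraction q of all entries occurs at delivery (assumed), the share is multiplied by 1 − q. For s = 4, e = 39:

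- q = 20%: 31% (20 weeks) and 39% (24 weeks).
- q = 40%: 23% and 29%.

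**Step 4, separating the two mechanisms.** Assume a 12% miscarriage risk from week 5 to a 24-week limit, with timing truncated exponential at 0.2 per week, entry uniform from week 5, and delivery at week 39. With u = weeks since week 5,

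F(u) = 0.12 × (1 − e^(−0.2u))/(1 − e^(−3.8)).

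- Losses after entry: ∫ from 0 to 19 of (0.12 − F) du = 0.548.
- Entrants still at risk: 19 × 0.88 + 0.548 = 17.268.
- Later entrants: 0.88 × (39 − 24 + 6) = 18.480.
- At-risk percentage: 0.548/17.268 = 3.17%.
- All-enrolled percentage: 0.548/35.748 = 1.53%.
- Check: share = 17.268/35.748 = 48.3%, and 3.17% × 48.3% = 1.53%.

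Late entry alone takes 12% to 3.2%, and the denominator takes it on to 1.5%. In absolute terms most of the shortfall is left truncation. Other timings give 6.4% at-risk and 3.1% all-enrolled (uniform), or 1.8% and 0.8% (0.4 per week).

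**Step 5, what could offset it.** Let r be the at-risk and s* the all-enrolled percentage. If a fraction f of the registry entered after a known loss, the all-enrolled figure equals r at f = (r − s*)/(1 − s*). At 0.2 per week this is (0.0317 − 0.0153)/(1 − 0.0153) = 1.67%. Across the three timings it is 0.9% to 3.3% (24-week limit). A small number of such entries would mask the dilution.

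**The case against.** The strongest reply is that the plan never chooses an all-enrolled denominator. That is correct. A reader might infer that Section 9 commits the registry to a diluted miscarriage rate; it does not, and a careful analyst could pick an at-risk denominator. What remains is that nothing requires one, and a bare at-risk percentage would still be left-truncated.

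A reader might also take one pattern, such as 39% to 49%, as the size of the effect. It is a single assumed entry pattern. Uniform entry fits poorly with selective testing and caesarean screening, and other patterns move the figure well outside that range.

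Nor does changing the denominator alone bring the figure up to a background rate. If the hazard doubled for four weeks after entry, under the same assumptions with a 24-week limit, the all-enrolled percentage would be 1.4% to 4.2% and the at-risk one 3.0% to 8.6%. Both are below the assumed 12%. The plan announces no comparison with a background rate, so this matters only if such a comparison is made.

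Two further points have weight. Gestational limits may stand in the appendices, which are listed by title only, so the request is to state them in Section 9, not a claim that they do not exist. And this is a descriptive registry with follow-up timed by gestation, so the denominators could probably be set at analysis without changing conduct. That limits the severity and also makes the correction cheap.

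**Conclusion.** The concern holds as a gap in the analysis plan. Section 9 gives pregnancy outcomes no risk set while entry is open throughout pregnancy and for six weeks after delivery, so a crude miscarriage percentage depends on entry timing through left truncation and, if all enrolled women are counted, through dilution. Under assumed uniform entry and a 20- or 24-week limit, the all-enrolled percentage is about 24% to 55% of the at-risk one, and lower if entry clusters at delivery.

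The downward direction relative to the at-risk figure is certain only if nobody enters after a known loss. Back-dated cases, published case reports and self-referral could bring in such women, so the documents do not show that the published figure would fall below the true risk. It is also tempting to extend the claim to preterm delivery. The sign of that effect is undetermined, because late entry lowers the percentage and selected cases may raise it, so it is not part of this conclusion.

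This should be corrected, but it does not invalidate the registry.

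**What to change.** In Section 9:

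- **(a) Miscarriage.** State the gestational limit. Use as denominator women infected before that limit whose pregnancy was ongoing at entry, and report by gestational age or trimester at infection.
- **(b) Whole-pregnancy risk.** Where such a miscarriage risk is quoted or set beside a background rate, use cumulative incidence on the gestational-age scale with delayed entry and a stated starting week.
- **(c) Preterm delivery and other birth outcomes.** Define the risk set by gestation at infection, not at enrolment. Women infected in pregnancy but enrolled after delivery, for example after a positive screen at caesarean section, are then kept, but shown separately as entered with the outcome known.
- **(d) Infection after delivery.** Keep these women out of pregnancy-outcome percentages and in the postnatal outcomes.

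The cost is mainly wording, plus a check that the forms record gestational age and the dates of infection, entry and outcome. Section 9 is purely descriptive here, so no clinical conduct changes.

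The price is precision. At the lower stated rate of 170 cases per month for 24 months (4,080 women, taken as an assumption), a share of 48% to 49% leaves about 1,950 to 2,000 women for miscarriage. Delayed-entry estimates from week 5 rest on small early risk sets: in simulation at 0.2 per week, the 95% range around a true 12% was about 8% to 20%. If infection changes the hazard, that curve also mixes recently and remotely infected women, so the results by gestation at infection should come first.
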